## 10.2. Secondary Analysis

Secondary efficacy analysis:

## **CLUE Overall Quality of Vision and Handling**

CLUE Overall Quality of Vision and Handling will be analyzed using the same statistical method described for CLUE Overall Comfort.

## **10.3.** Other Analysis

Daily Average Wear Time, Subject reported ocular symptoms and lens fitting characteristics will be descriptively summarized at the two-week follow-up evaluation by lens type.

## 11. SAFETY EVALUATION

## 11.1. Adverse Events

Listings of all reported ocular and non-ocular AEs and SAEs will be reported and will include lens type, eye diagnosis, severity of the AE, the number of days the subject spent in the study, the slit lamp findings at discovery of the AE, whether or not it is lens related, the possible cause, and treatments provided to the patient, the outcome, the subjects final Snellen visual acuity, whether or not the subject eye had a scar at the resolution of the AE and the action taken. In addition, the total number of subjects and the total number of eyes with each type of AE (SAEs, ocular AEs and non-ocular AEs) will be tabulated and presented as a footnote in each summary.

## 11.2. Keratometry and Over Refraction

Keratometry will be assessed for each eye at Entrance (Visit 1) and Exit (Visit 2) for the following metrics: (1) Steep Dioptric Power, (2) Steep Degrees, (3) Flat Dioptric Power and (4) Flat Degree. Each keratometry metric will be summarized using n, mean, min, and max across eye type.

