7.2. Detailed Study Procedures

VISIT 1

The subjects must present to Visit 1 wearing their habitual contact lenses.

	Visit 1: Screening			
Step	Procedure	Details		
1.1	Statement of Informed Consent	Each subject must read, understand, and sign the Statement of Informed Consent before being enrolled into the study. The Principal Investigator or his/her designee conducting the informed consent discussion must also sign the consent form.		
r.		Note : The subject must be provided a signed copy of this document.		
1.2	Demographics	Record the subject's date of birth, gender, race and ethnicity.		
1.3	Medical History and Concomitant Medications	Questions regarding the subjects' medical history and concomitant medications.		
1.4	Habitual Lenses	Questions regarding the subject's habitual lens type and parameters.		
1.5	Eligibility after Screening	All responses to Screening Inclusion Criteria questions must be answered "yes" and all responses to Exclusion Criteria must be answered "no" for the subject to be considered eligible.		

	Visit 1: Screening			
Step	Step Procedure Details			
		If the subject is deemed to be ineligible after screening, proceed to Final Evaluation and complete Subject Disposition. Refraction and Biomicroscopy forms are not required.		

	Visit 1: Baseline			
Step	Procedure	Details		
1.6	Baseline Questionnaire	The subject will respond to the CLUE Baseline Questionnaire.		
1.7	Entrance Visual Acuity	Record the distance Snellen visual acuity (OD, OS, and OU) to the nearest letter with their habitual contact lens correction in place. Subjects must read the smallest line until at least 50% of the letters are read incorrectly.		
1.8	Remove Habitual Lens	The subject's habitual lenses will be removed and stored in their own lens case. If they forgot to bring their lens case, one will be provided to them.		
1.9	Iris Color	The investigator will record the subject's iris color based on the scale provided.		
1.10	Keratometry	Record the keratometry readings OD and OS in diopters. This can come from any appropriate instrument so long as the same instrument is used at the Final Evaluation.		
1.11	Subjective Sphero- cylindrical Refraction	Complete subjective spherocylindrical refraction and record the resultant distance visual acuity (OD, OS, and OU) to the nearest letter. Best corrected distance visual acuity (BVA) must be 20/25+3 or better in each eye.		

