#### Secondary Objective:

The secondary objective of this study is to demonstrate that the Test lens is equal or better than marketed product senofilcon A (ACUVUE® OASYS, Johnson & Johnson Vision Care, Inc.) with regards to overall CLUE vision and handling.

Other observations of interest include adverse events, keratometry, surface characteristics (deposits and wettability), daily wear time, reasons for discontinuation, and lens damage.

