## 2. STUDY DESIGN

### 2.1. Overview

This study is a randomized, 2-visit, partially subject-masked, 2-arm parallel, dispensing trial. Approximately 236 subjects (118 subjects /arm) will be screened and enrolled to ensure that at least 224 subjects (112 subjects/arm) complete the study.

The study begins with an initial visit (Visit 1). If a subject is found to meet all eligibility criteria, they will be randomized to one of two study lenses (Test or Control) in a bilateral fashion.

If the subject is dispensed study lenses at the initial visit, one follow-up visit will be conducted. The follow-up visit will occur approximately two weeks after the initial visit. Unscheduled follow-up visits may occur during the study. Subjects will be advised to wear the study lenses at least five (5) days per week for at least six (6) hours per day for a period of two weeks. There is no planned lens replacement scheduled during this study.

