#### 7.2. **Summary Statistics**

Throughout the analysis of data, the results for each subject/eye will be used when available for summarization and statistical analysis. Unscheduled visits will be summarized separately and will be excluded from the efficacy statistical analysis but will be included in the analysis of safety endpoints (slit lamp findings and lens fitting).

Summary tables (descriptive statistics and/or frequency tables) will be provided for all baseline variables, efficacy variables and safety variables as appropriate. Continuous variables will be summarized with descriptive statistics (n, mean, standard deviation [SD], median, minimum and maximum). Frequency count and percentage of subjects or eyes within each category will be provided for categorical data.

Safety variables will be summarized on both safety and PP populations whereas efficacy variables will be summarized on the PP and ITT populations.

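### SAP 11.2 takes ordinary means, minima and maxima of keratometry axes, which cannot be interpreted when the axes cluster near 0/180 degrees

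*SAP*

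**What the plan says.** SAP 11.2, within the safety evaluation, plans keratometry for each eye at the entrance and exit visits. The metrics are "1) Steep Dioptric Power, (2) Steep Degrees, (3) Flat Dioptric Power and (4) Flat Degree". The summary is the same for all of them: "Each keratometry metric will be summarized using n, mean, min, and max across eye type".

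The general rule in SAP 7.2 makes no exception for angles: "Continuous variables will be summarized with descriptive statistics (n, mean, standard deviation [SD], median, minimum and maximum". Neither section names an axial or circular mean, a power-vector conversion, or a within-eye change for keratometry.

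The protocol's instruction to sites (Section 7.2, step 1.10, repeated at step F.2 of the Final Evaluation) is "Record the keratometry readings OD and OS in diopters". It requires the same instrument at both visits and does not mention an axis in degrees.

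Keratometry is descriptive. SAP 1.1 says: "Other observations of interest include adverse events, keratometry, surface characteristics (deposits and wettability". It is not in the lists of other endpoints (Protocol 2.2.3, SAP 3.3), and no hypothesis refers to it.

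**The concern.** A corneal meridian is an axis on a 180-degree circle, so readings of 1 and 179 are neighbours. An ordinary mean treats them as almost the whole scale apart. On the plain reading of SAP 11.2, the programmer will average the recorded degrees directly. If one group of axes (steep or flat) clusters near horizontal, the table could then print a mean meridian perpendicular to the real one. Set beside the exit value, it could also suggest a rotation that did not happen, or reverse one that did. At stake is the accuracy of two descriptive columns in the safety section.

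**Working it through.** **Plan's own figure.** The documents state no keratometry result or axis distribution, so there is nothing to reproduce.

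**Inputs from the documents.** Two axis metrics are summarised by mean, minimum and maximum (SAP 11.2). The completion target is "at least 224 subjects (112 subjects/arm) complete the study" (SAP 2.1), so one arm gives 112 × 2 = 224 eyes.

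**Assumptions, not in the documents.** Axes are recorded on a 0 to 180 scale, are normally spread around a centre c with SD s of 10, 15 or 20 degrees, and are independent between eyes. Centres tried: 0, 10, 20, 45 and 90.

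**Correct average.** Double each angle, average the sines and cosines, take the angle of the result and halve it. The error is the shorter way round between this and the ordinary mean, so it cannot exceed 90.

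**Hand examples.**
- Axes 5 and 175: ordinary mean (5 + 175)/2 = 90. Doubled angles are 10 and 350, whose average direction is 0, so the axial mean is 0/180. Error 90.
- Axes 5, 5 and 175: ordinary mean 185/3 = 61.7; axial mean 1.7. Error 60.
- Axes 85 and 95: both means are 90. Error 0.

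**Why the centre matters.** An eye whose axis falls just below 0 is recorded 180 too high. For centres of 0 to 90 with these SDs, the expected ordinary mean is therefore about c + 180 × Φ(−c/s). With s = 15:
- c = 10: Φ(−0.667) = 0.2525, so 10 + 45.4 = 55.4, an error of about 45.
- c = 20: Φ(−1.333) = 0.0912, so 20 + 16.4 = 36.4, an error of about 16.
- c = 0: Φ(0) = 0.5, so the mean is about 90. In single samples it varies around 90, which brings the average error to 85.

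**Apparent rotation.** If every axis turns by +10, the eyes recorded between 170 and 180 pass the wrap and drop by 180. At c = 0 and s = 15 their share is Φ(0) − Φ(−10/15) = 0.5 − 0.2525 = 0.2475. The ordinary mean therefore moves by 10 − 180 × 0.2475 = −34.6. The axial mean moves by +10.0.

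**Simulation, 1,000 samples of 224 eyes per setting** (degrees; values for SD 10 / 15 / 20):

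| Centre | Average error of ordinary mean | Change shown for a true +10 rotation |
|---|---|---|
| 0/180 | 85.4 / 85.0 / 85.1 | −51.4 / −34.6 / −24.5 |
| 10 | 28.4 / 45.3 / 55.6 | −14.4 / −19.1 / −17.1 |
| 20 | 4.0 / 16.4 / 28.4 | +6.2 / −2.3 / −6.4 |
| 45 | 0.0 / 0.3 / 2.1 | +10.0 / +9.8 / +8.4 |
| 90 | 0.0 / 0.1 / 0.2 | +10.0 / +10.0 / +10.0 |

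The axial mean moved by +10.0 in every row. At centre 0 and SD 15, the 95% range of the change shown was −45 to −25, and the minimum and maximum averaged about 0 and 180. With no true rotation and only reading noise of SD 5 (assumed), the ordinary mean moved by −7.3 to +6.7 (95% range) at centre 0, against −0.7 to +0.7 at centre 90.

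**The case against.** A reader might infer that the planned summary cannot show a corneal change at all, or that half of it is wrong. The documents do not support either reading.

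- The steep and flat powers are summarised at both visits and have no wrap. Over the same eyes, mean (steep − flat) = mean steep − mean flat, so steepening, flattening and a change in the average amount of toricity can all be read from the planned means. Only the orientation of the astigmatism is affected.
- If flat meridians sit near 180 and steep meridians are perpendicular to them, the steep mean near 90 is correct. One metric of the four then fails, not two.
- The size depends on where the axes cluster, which the documents do not give. The 90-degree figure is the maximum. At centres 45 and 90 the ordinary mean is close to right and follows a rotation, nearly or exactly.
- No purpose is stated for keratometry beyond its listing as an observation. Requiring the same instrument at both visits suggests a comparison, but that is an inference.
- Since the protocol asks only for dioptres, it is not established that axes will be recorded.

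These limits stand. They do not rescue the sentence in SAP 11.2, which applies the same statistics to degrees as to powers and has no safeguard for axes near 0/180. Nor can that case be set aside as unlikely: if steep and flat meridians are about 90 degrees apart (an assumption), then whenever one group clusters near 90 the other sits at the wrap.

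**Conclusion.** The point holds in a limited form and is minor. As written, the mean, minimum and maximum of Steep Degrees and Flat Degree are not interpretable when those axes cluster near 0/180. The mean can then be up to 90 degrees from the axial mean, and a rotation can be shown with the wrong size and sign. Over the assumed SDs of 10 to 20 degrees, the average error is about 85 degrees at centre 0/180, 28 to 56 at centre 10, 4 to 28 at centre 20, and at most about 2 at centres 45 and 90. These sizes rest entirely on assumed axis distributions and independent eyes; the wrap itself needs no distributional assumption. The effect is confined to descriptive axis columns in the safety section.

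**What to change.** In SAP 11.2, keep the planned count, mean, minimum and maximum for the two power metrics only. For the two degree metrics, replace them with one of the following, at Visit 1 and Visit 2 by lens:

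- a doubled-angle axial mean; or
- a conversion of each eye's reading to mean power, J0 and J45, which can be averaged in the ordinary way. With steep power S, flat power F and steep meridian α: mean power = (S + F)/2, J0 = ((S − F)/2) cos 2α and J45 = ((S − F)/2) sin 2α. The sign convention should be stated.

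The first option is enough to correct the error. A within-eye change from Visit 1 to Visit 2 would be a useful addition but is not needed for that.

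Also reconcile SAP 11.2 with Protocol 7.2 (steps 1.10 and F.2), so that axes are recorded if they are to be summarised; if they are not recorded, the two degree metrics should be removed from the SAP.

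The cost is a sentence or two in the SAP and a few lines of code if the axes are already captured. If they are not, a clarification of the recording instruction is needed as well.

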# 11.3. Contact lens Corrected Visual Acuity

Contact lens visual acuity will be assessed using Snellen visual acuity Charts at both the fitting evaluation and the 2-week Follow-up. CLVA will be assessed both monocularly and binocularly. Summaries for Monocular CLVA and binocular CLVA will be presented using counts and percentages of eyes and subjects, for monocular CLVA and binocular CLVA, respectively. A detailed listing of eyes that have worsened by 2 or more lines at final visit compared to baseline will be presented.

## 11.4. Reasons for Discontinuation

The number of discontinued subjects by the analysis time point will be displayed by visit. Reasons for discontinuation include the following:

- 1. Adverse Event
- 2. Unsatisfactory lens fitting due to test article
- 3. Unsatisfactory visual response due to test articles
- 4. Lens discomfort
- 5. Withdrew consent during study
- 6. Lost to follow-up
- 7. Subject no longer meet eligibility criteria
- 8. Subject withdrawn by PI due to non-compliance to protocol
- 9. Test article no longer available
- 10. Other

## 11.5. Unscheduled Lens Replacement

The number of unscheduled lens replacements and corresponding reasons will be tabulated by visit and overall across eyes for both completed and discontinued eyes.

## **11.6.** Physical Examination Findings

Slit lamp findings will be assessed for each subject eye at baseline, the 2-week follow-up and at any unscheduled visit using the FDA Grading scale (Grade 0=None, Grade 1=Trace, Grade2=Mild, Grade 3=Moderate, Grade 4=Severe). Slit lamp finding assessments include the following metrics:

- Corneal Infiltrates (Yes/No)
- Corneal Edema
- Corneal Neovascularization
- Corneal Neovascularization Location
- Corneal Staining
- Corneal Staining Location
- Conjunctival Injection
- Tarsal Abnormalities
- Other

## 11.7. Clinical Laboratory Tests

Not applicable.

### 11.8. Other Safety Parameters

Subject's Reported Ocular Symptoms

Frequency and severity by eye of subject's reported ocular symptoms and problems with the study lens at fitting and post-fitting evaluation visits including the 2-Week Follow-up and unscheduled visits. Severity of the symptoms can be:

- 0 = Not Applicable or Not Recorded;
- 1 = Mild and results in little or no interference with lens wear;
- 2 = Moderate AND/OR occasionally interferes with lens wear;
- 3 = Severe AND/OR frequently interferes with lens wear.

The related procedure is explained in CTP-2009 in Appendix D of the study protocol.

## Lens fitting characteristics

Frequency by eye of mechanical lens fitting characteristics at fitting and 2-Week Follow-up evaluations. Lens fitting characteristics to be reported are:

- Lens Centration Grade
- Decentered Direction
- Limbal Exposure Grade
- Edge Lift (Present or Absent)
- Primary Gaze Movement Grade
- Upgaze Movement Grade
- Lens Tightness Grade (Push-up Test)
- Acceptable Fitting (yes/no)

## Contact Lens Deposits

Contact lens deposits will be assessed for each eye at the 2-week Follow-up on the front and back surface of the study lens; the amount of deposits will be Graded using the scale:

- None = Grade 0 (No deposition).
- Slight = Grade 1 (Deposition which occupies 1-5% of the lens surface area.)
- Mild = Grade 2 (Deposition which occupies 6-15% of the lens surface area.)
- Moderate = Grade 3 (Deposition which occupies 16-25% of the lens surface area.)
- Severe = Grade 4 (Deposition which occupies =26% of the lens surface area.)

## Contact Lens Wettability

Contact lens Wettability will be assessed for each eye at both lens fitting and the 2-week Followup. Wettability will be Graded using the scale:

- Grade 0 = All regions of lens surface are wettable between blinks (a minimum of 6 seconds between blinks).
- Grade 1 = Discrete non-wetting area(s) after a minimum of 3 seconds post blink.
- Grade 2 = Single non-wetting area within 2-3 seconds of blink.
- Grade 3 = Several non-wetting areas within 2-3 seconds of blink.
- Grade 4 = Immediate area(s) of non-wetting after blink.

#### 14. SAS CODE

### 14.1. Primary Endpoints

```
Distance Visual Acuity (logMAR)

PROC MCMC DATA =ads vp NTHREADS=8 SEED=20180906 NBI=100000 NMC=800000

THIN=100 DIAG=ALL OUTPOST= simout DIC PLOTS(SMOOTH FRINGE)=ALL

MCHISTORY=BRIEF PROPCOV=QUANEW STATS=ALL STATS(ALPHA = (0.05)

PERCENTAGE=(2.5 50 97.5))

plots(smooth) = all monitor = ( parms mu C mu T diff);
```

PARMS beta0 0; PARMS beta1 0 beta2 0 beta3 0 beta4 0; PARMS s2 1; PARMS s2g\_site 1 s2g\_subj 1;

```
PRIOR beta: ~ NORMAL(0, var = 1000);
PRIOR s2 ~ IGAMMA(.001, s =.001);
PRIOR s2g_site s2g_subj ~ IGAMMA(.001, s =.001);
```

```
RANDOM Gamma site ~ NORMAL(0, var = s2g site) SUBJECT=siteid;
RANDOM Gamma subj ~ NORMAL(0, var = s2g subj) SUBJECT=site subjid;
mu = beta0 + beta1*TRTAN + beta3*age +beta4*sexn + Gamma_site + Gamma_subj;
MODEL AVAL ~ normal(mu, var = s2);
```

```
BEGINNODATA;
```

```
mu C = beta0 + 0.5* beta4;
mu T = beta0 + beta1 + 0.5* beta4;
diff = mu T - mu_C;
ENDNODATA;
RUN;
```

```
Where,
ads vp =analysis data set for Distance Monocular Visual Acuity (logMAR)
trtan= numerical representation of treatment, where Test=1 and Control=0
bASE= Baseline CLUE comfort score
age= Age of subject at time of consent
sexn= Numerical representation of sex, where Female=1 and Male=0;
siteid= Site Number
site_subjid=Unique Subject ID
```

```
CLUE Comfort
```

```
PROC MCMC DATA = ads cmt NTHREADS = 8 SEED=198756325 nbi=100000 nmc
=800000 thin=100 DIAG =ALL OUTPOST=simout DIC PLOTS(SMOOTH FRINGE)= ALL
MCHISTORY = BRIEF PROPCOV =QUANEW STATS=ALL STATS(ALPHA=(0.05)
PERCENTAGE=(2.5 50 97.5))plots(smooth)=ALL MONITOR=(_parms_mu_C mu_T diff);
PARMS beta0 60;
```

```
CR-6305, Statistical Analysis Plan Version 1.0
```

PARMS beta1 0 beta2 0 beta3 0 beta4 0; PARMS s2 400; PARMS s2g\_site 1;

PRIOR beta: ~ NORMAL(0, var = 1000); PRIOR s2 ~ IGAMMA(.001, s =.001); PRIOR s2g\_site ~ IGAMMA(.001, s =.001);

random Gamma\_site ~ NORMAL(0, var = s2g\_site) SUBJECT=SITEID;

mu = beta0 + beta1\*TRTAN + beta2\*base + beta3\*age + beta4\*sexn + Gamma\_site;

```
MODEL AVAL ~ normal(mu, var = s2);
```

```
BEGINNODATA;
mu C = beta0 + 0.5* beta4;
mu T = beta0 + beta1+ 0.5* beta4;
diff = mu_T - mu_C;
ENDNODATA;
RUN;
```

Where, ads\_cmt=analysis data set for CLUE Comfort trtan= numerical representation of treatment, where Test=1 and Control=0 bASE= Baseline CLUE comfort score age= Age of subject at time of consent sexn= Numerical representation of sex, where Female=1 and Male=0; siteid= Site Number

Vision Satisfaction in Bright Lighting

```
PROC MCMC DATA =ads VS SEED=20181019 nbi =100000 nmc =500000 thin=100
DIAG=ALL OUTPOST=simout DIC PLOTS(SMOOTH FRINGE) = ALL
MCHISTORY=BRIEF PROPCOV=QUANEW STATS=ALL STATS(ALPHA=(0.05)
PERCENTAGE = (2.5 50 97.5))
plots(smooth)=ALL MONITOR=(_parms_OR);
```

ARRAY theta[4] theta1-theta4; ARRAY gamma[4] gamma1-gamma4;

PARMS theta1-theta4 beta0 0 beta1 0 beta2 0 beta3 0; PARMS s2g 1;

PRIOR beta: ~ NORMAL(0,VAR=1000); PRIOR theta1 ~ NORMAL(0,VAR=100); PRIOR theta2 ~ NORMAL(0,VAR=100,lower=theta1); CR-6305, Statistical Analysis Plan Version 1.0

```
PRIOR theta3 ~ NORMAL(0,VAR=100,lower=theta2);
PRIOR theta4 ~ NORMAL(0,VAR=100,lower=theta3);
PRIOR s2g ~ IGAMMA(.01, s =.01);
```

```
RANDOM Gamma site ~ NORMAL(0, VAR = s2g) SUBJECT=SITEID;

mu = beta0 + beta1*TRTAN + beta2*age + beta3*sexn + Gamma_site;

DO j = 1 to 4;

gamma[j] = logistic(theta[j] + mu);

END;

pi1 = gamma1;

pi2 = gamma2 - gamma1;

pi3 = gamma3 - gamma2;

pi4 = gamma4 - gamma3;

pi5 = 1 - sum(of pi1-pi4);
```

```
llike = logmpdfmultinom(of y1-y5, of pi1-pi5);
MODEL DGENERAL(llike);
```

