## 4. STATISTICAL HYPOTHESES FOR STUDY OBJECTIVES

#### 4.1. Primary Hypotheses

All the primary hypotheses must be met in order to satisfy the primary objective of this study.

- 1. Subjects wearing the JJVCI Investigational contact lenses on a daily wear basis will have patient reported comfort at the 2-Week Follow Up visit that is non-inferior to that of subjects wearing predicate device on a daily wear basis. A non-inferiority margin of -5 CLUE points will be used.
- 2. Subjects wearing the JJVC Investigational contact lenses on a daily wear basis will report distance monocular visual acuity (logMAR: bright room luminance / high contrast charts) at the 2-Week Follow Up visit that is non-inferior to that of subjects wearing predicate device on a daily wear basis. A non-inferiority margin of 0.05 LogMAR will be used.
- 3. Subjects wearing the JJVCI Investigational contact lenses on a daily wear basis will have patient reported outcome (Agree and Strongly Agree) on the Quality of Vision in Bright Light at the 2-Week Follow Up visit that is non-inferior to that of subjects wearing predicate device on a daily wear basis. A non-inferiority margin of 10% will be used.
- 4. Subjects wearing the JJVC Investigational contact lenses on a daily wear basis will have a percentage of any grade 3 or higher slit lamp findings at all visits (scheduled and unscheduled) that is non-inferior to that of subjects wearing predicate device on a daily wear basis. A non-inferiority margin of 5% will be used.
- 5. At least 90% of eyes wearing the JJVC Investigational contact lenses on a daily wear basis will have acceptable fits across the fitting and follow-up visits.

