## 7.5. Statistical Significance Level

All planned analysis will be conducted with an overall type I error rate of 5%. There will be neither adjustment for multiple tests nor adjustment for multiplicity of endpoints. Unless otherwise specified, all statistical tests will be 2-sided.

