#### Hypothesis Testing

The null and alternative hypotheses for non-inferiority are as follows:

$$\begin{array}{l} H_0 \ p_T - \ p_C \leq -0.1 \\ H_A \ p_T - \ p_C > -0.1 \end{array}$$

Where  $p_T$  and  $p_C$  are the proportions of patients with positive response (agree or strongly agree) in the Test group and Control group, respectively. Non-inferiority will be declared if the lower bound of the 2-sided 95% credible confidence interval is above -0.1 i.e.  $P(p_T - p_C > -0.1)=0.975$ .

Primary Safety Analysis:

Safety analysis will be conducted on safety population by actual treatment received by subjects.

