#### **BEGINNODATA;**

```
array gammac[5];
  array gammat[5];
  array pc[5];
  array pt[5];
  DO i = 1 to 5;
   gammac[i] = logistic(theta[i] + beta0 + 0.5*beta3);
   gammat[i] = logistic(theta[i] + beta0 + beta1 + 0.5*beta3);
  END;
 pc1 = gammac1;
 pc2 = gammac2 - gammac1;
 pc3 = gammac3 - gammac2;
 pc4 = gammac4 - gammac3;
 pc5 = 1 - sum(of pc1-pc4);
 pt1 = gammat1;
 pt2 = gammat2 - gammat1;
 pt3 = gammat3 - gammat2;
 pt4 = gammat4 - gammat3;
 pt5 = 1 - sum(of pt1-pt4);
 p2box c = pc1 + pc2;
 p2box t = pt1 + pt2;
 diff = p2box t - p2box c;
ENDNODATA:
RUN;
```

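### The SAP program for the bright-light co-primary does not return the difference its decision rule tests, and it predicts at age 0; correct it before lock

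*SAP*

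**What the plan says.** SAP 4.1 lists bright-light satisfaction among five primary hypotheses that must all be met, and for this one "A non-inferiority margin of 10% will be used". In SAP 10.1, p_T and p_C "are the proportions of patients with positive response (agree or strongly agree"), and the rule is "Non-inferiority will be declared if the lower bound of the 2-sided 95% credible confidence interval is above -0.1". The model there has four intercepts (X = 1 to 4), a lens effect and a random site effect. It has no separate overall intercept. Age and sex may be added when appropriate. The same section says the analysis is to give the odds ratio of a higher rating with Test.

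The program is in SAP 14.1. It declares "ARRAY theta[4] theta1-theta4" and sets up parameters with "PARMS theta1-theta4 beta0 0 beta1 0 beta2 0 beta3 0". The fitted linear predictor is beta0 + beta1·treatment + beta2·age + beta3·sex + site. In the prediction block the loop runs i = 1 to 5, and its control-arm line is "gammac[i] = logistic(theta[i] + beta0 + 0.5*beta3"). The block then forms the top-two-box proportions and their difference, `diff`. The monitor list is "plots(smooth)=ALL MONITOR=(_parms_OR").

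SAP section 1 makes the SAP the final guidance and lets it supersede the protocol's statistical section.

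**The concern.** The program should be the exact form of the plan for a must-pass endpoint. As printed it does not deliver the quantity on which that endpoint is judged, and part of it refers to something that does not exist. The acuity and comfort programs in the same section do monitor `diff`, so this one departs from the SAP's own pattern.

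The age omission is less visible and would survive a repair of the other faults. A corrected program would run and print a difference, but for an age outside the trial population, and nothing in the output would show it.

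**Working it through.** **1. Monitor list against assigned quantities.** The quantities given values in the program are theta, beta, s2g, mu, gamma, pi, llike, gammac, gammat, pc, pt, p2box_c, p2box_t and diff. OR is not among them. The monitor list holds the parameters and OR, not diff. The missing space in the printed list is probably a text-extraction effect and is not counted; OR is unassigned under either reading.

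**2. Loop bound against array length.** theta has 4 elements; gammac and gammat have 5. The loop to 5 requests `theta[5]`. The fifth pass is not needed:
- pc5 and pt5 come by subtraction.
- p2box_c = pc1 + pc2 = gammac1 + (gammac2 − gammac1) = gammac2, and likewise p2box_t = gammat2.

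**3. What the decision quantity reduces to.** As coded:
- p_C = logistic(theta2 + beta0 + 0.5·beta3)
- p_T = logistic(theta2 + beta0 + beta1 + 0.5·beta3)
- diff = p_T − p_C

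beta2·age appears in the fit but in neither line. In the acuity and comfort programs the same omission cancels, because there diff = beta1. Here it does not cancel.

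**4. Size of the age effect.** First, the plan's own figure: the sizing text's odds-ratio margin is (0.4/0.6)/(0.5/0.5) = 0.667, matching the stated 0.67. That equals −10 points only at a 50% control rate. Write η for the control linear predictor. With the odds ratio held at 0.67, diff = logistic(η + ln 0.67) − logistic(η):

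| η | control proportion | diff |
|---|---|---|
| 0 | 0.500 | −0.099 |
| 0.5 | 0.622 | −0.098 |
| 1.1 | 0.750 | −0.082 |
| 2 | 0.881 | −0.049 |
| 3 | 0.953 | −0.022 |

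The row η = 1.1 is close to the historical control rate in SAP Table 10, (51 + 130)/242 = 74.8%. Dropping beta2·age moves η. The documents give no beta2, so any value is an assumption. A slope of −0.03 per year over 30 years would move η by 0.9, from 1.1 to 2, and the reported diff from −0.082 to −0.049.

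Put the other way, the odds ratio that sits exactly at −0.10 is:
- control 0.748: (0.648/0.352)/(0.748/0.252) = 0.62
- control 0.881: (0.781/0.219)/(0.881/0.119) = 0.48

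So the same lens effect can pass or fail according to the age at which it is evaluated. If beta2 is near zero, the effect is negligible.

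**5. The repaired formula gives the needed output.** Table 10 rates were scaled to 112 per arm and fitted by proportional odds without site, age or sex, with 20,000 normal-approximation draws. diff had median 0.080, 95% interval −0.002 to 0.165, and P(diff > −0.1) about 1.0. This illustrates the output; it does not predict the trial result.

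**6. The extra intercept.** Adding a constant to beta0 and subtracting it from every theta leaves the likelihood unchanged. Only theta2 + beta0 enters diff, so diff is unaffected.

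**The case against.** The best defence is that these are routine coding slips around a rule that is fully stated, and most of it stands. Several stronger readings are tempting but not supported.

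- **That the analyst could choose the estimand after unblinding.** SAP 4.1 and 10.1 fix the response, the difference scale, the margin and the 95% interval. The 0.67 odds-ratio margin appears only in the sizing text. No section says the program will first be run on unmasked data. Protocol 5.2 aims to keep the biostatistician and data management unaware of assignment, and SAP section 1 and protocol 14.10 require changes to be documented.
- **That an odds ratio would be reported in place of the difference.** An unassigned OR cannot be output.
- **That the decision can never be made.** The program saves its posterior draws (OUTPOST). Once a run completes, diff can be rebuilt from theta2, beta0, beta1 and beta3, so leaving it out of the monitor list loses no information. The loop bound and the unassigned OR are the obstacles to a run, and such a failure would be visible.
- **That the redundant beta0 undermines the result.** It may slow mixing of the individual parameters, but the priors are proper and diff stays identified.
- **That the slit lamp program fails in the same way.** It does not monitor its Diff, but it does monitor P_C and P_T and saves the draws, so Diff is one subtraction per draw.

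None of this answers the three mismatches in the printed code or the age term. Lost underscores and spaces in the extracted text cannot explain a bound of 5 on an array of 4, an unassigned symbol or an absent `diff`.

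**Conclusion.** Wrong as written. The printed program for a must-pass endpoint does not return the interval its decision rule needs, because OR is never assigned, `diff` is not monitored and `theta[5]` does not exist. If only those faults are repaired, `diff` still refers to age 0 unless age is centred. At an odds ratio of 0.67 the difference ranges from −0.099 to −0.022 over control rates of 50% to 95%. The actual shift depends on an age slope the documents do not give.

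The estimand and margin are settled in SAP 10.1, so this is a correction to make before lock and not an open analysis choice. The mismatches are read directly from the text. The program was not run in SAS, and how SAS would respond to the bad subscript or the unassigned symbol is an expectation, not a tested result.

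**What to change.** In the SAP 14.1 bright-light program:

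1. Run the prediction loop over i = 1 to 4.
2. Use `MONITOR=(_parms_ p2box_c p2box_t diff OR)` and define OR = exp(beta1), since SAP 10.1 asks for the odds ratio. With category 1 coded as Strongly Agree, this is the odds of a higher rating with Test.
3. Centre age, or add beta2 times a stated reference age to both gammac and gammat, and record the value in the SAP.
4. Remove beta0 to match the SAP 10.1 model. This helps mixing and does not change the likelihood for diff.
5. Dry-run on dummy data before database lock and confirm that the output contains the 95% interval for diff.

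Two small items fit the same edit. Add Diff to the slit lamp monitor list as a convenience, and carry the age correction over, because P_C and P_T there also omit a fitted age term. Reconcile the site-variance prior, which is inverse-gamma(0.001, 0.001) in SAP 10.1 but uses 0.01 in the bright-light code.

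The cost is a few lines of code and one dry run. Sample size, data collection and the decision rule do not change.
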